Pembrolizumab Administration at Site		X	X	X	X	X			Cycle 1 treatment should be given within 5 days of randomization.
Dispense Epacadostat (Group 1 only)		X	X	X	X	X			
Epacadostat Administration at Site (Group 1 only)		X	X						Only morning dose will be administered at site.
Collect and Count Remaining Epacadostat (Group 1 only)			X	X	X	X	X		
Efficacy Procedures/Assessments									
Tumor Imaging and RECIST Assessments	X				X		Per Standard of Care		Imaging should be performed at Week 9 (+7 days) after randomization. Thereafter imaging is to be performed as per SoC for the disease and local guidelines; only the date of scans performed as per SoC needs to be documented in the eCRF. Schedule should be followed regardless of treatment delays.

Study Period	Screen	Treatment (3-week cycles)					EOT	Post-treatment	Notes
Treatment Cycle/Title	Screen (V 1)	1	2	3	4	Cycle 5 to Cycle 35	Discon	Safety FU	
Scheduled Window (Days):	-28 to -1	+5	±3	±3	±3	±3	At treatment discon	30 days after last dose (+7 days)	Assessments/procedures are to be performed on Day 1 and prior to the first dose of treatment for each cycle unless otherwise specified. Participants who discontinue study treatment for whatever reason will proceed directly to EOT and Safety Follow-up.
Safety Procedures/Assessments									
Full Physical Examination	X						X		
Directed Physical Examination		X	X	X	X	X		X	
Height	X								
Vital Signs and Weight	X	X	X	X	X	X	X	X	Vital signs to include temperature, pulse, respiratory rate and blood pressure.
ECOG PS	X	X	X	X	X	X	X	X	ECOG PS is to be performed within 7 days of randomization and must be 0 or 1 on the first day of dosing.
12-lead ECG (Local)	X						X		ECGs at screening and EOT are required for all participants. ECGs should also be done when clinically indicated.
12-lead ECG (Local; Group 1 at select sites only)		X	X						Predose and 2 hours (±15 minutes) after the morning dose of epacadostat.
Pregnancy Test Serum or Urine (WOCBP only)	X								WOCBP require negative test within 72 hours prior to Cycle 1 Day 1. Monthly (ie, before each cycle) pregnancy testing should be conducted as per local regulations where applicable.
Coagulation	X								Any participant receiving anticoagulant therapy should have coagulation factors monitored closely throughout the study.

Study Period	Screen	Treatment (3-week cycles)					EOT	Post-treatment	Notes
Treatment Cycle/Title	Screen (V 1)	1	2	3	4	Cycle 5 to Cycle 35	Discon	Safety FU	

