#### 9.3.1 Time Period and Frequency for Collecting AE, SAE and Other Reportable Safety Event Information

All AEs, SAEs and other reportable safety events that occur after the consent form is signed but before treatment allocation/randomization must be reported by the investigator if the participant is receiving placebo run-in or other run-in treatment, if the event cause the participant to be excluded from the trial, or is the result of a protocol-specified intervention, including but not limited to washout or discontinuation of usual therapy, diet, or a procedure.

- All AEs from the time of treatment allocation/randomization through 30 days following cessation of study treatment must be reported by the investigator.
- All AEs meeting serious criteria, from the time of treatment allocation/randomization through 90 days following cessation of study treatment, or 30 days following cessation of study treatment if the participant initiates new anticancer therapy, whichever is earlier must be reported by the investigator.

The investigator must report all pregnancies and exposure during breastfeeding from the time of treatment allocation/randomization through

- 120 days following last dose of pembrolizumab and/or epacadostat OR
- 180 days after last dose of chemotherapeutic agents OR
- 30 days following cessation of study treatment if the participant initiates new anticancer therapy.

Additionally, any SAE brought to the attention of an investigator at any time outside of the time period specified above must be reported immediately to MSD if the event is considered to be drug-related.

Investigators are not obligated to actively seek AE or SAE or other reportable safety events in former study participants. However, if the investigator learns of any SAE, including a death, at any time after a participant has been discharged from the study, and he/she considers the event to be reasonably related to the study treatment or study participation, the investigator must promptly notify MSD.

All initial and follow-up AEs, SAEs and other reportable safety events will be recorded and reported to MSD or designee within the timeframes as indicated in [Table 15](#).

Table 15 Reporting Time Periods and Timeframes for Adverse Events and Other Reportable Safety Events

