### **9.5.1 Physical Examinations**

#### **9.5.1.1 Full Physical Exam**

The investigator or qualified designee will perform a full physical exam as per institutional standard during the screening period. Clinically significant abnormal findings should be recorded as medical history. The time points for full physical exams are described in Section 2 - SoA. After the first dose of study treatment, new clinically significant abnormal findings should be recorded as AEs.

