### **9.5.3 Electrocardiograms**

Baseline ECGs will be obtained at screening with additional ECGs obtained at EOT, and as clinically indicated for all participants. At select centers only, additional ECGs will also be obtained from Group 1 participants at Cycle 1 Day 1 predose and 2 hours ( $\pm$  15 minutes) after the first dose of epacadostat and Cycle 2 Day 1 predose and 2 hours ( $\pm$  15 minutes) after administration of epacadostat. The ECG measurement should always be performed prior to the PK sample blood draw if both are scheduled at the same nominal planned timepoint. Clinically significant abnormal findings prior to signing consent should be recorded as

medical history. Clinically significant abnormal findings after signing consent should be recorded as an AE.

The ECGs will be interpreted by the investigator at the site and will be used for immediate participant management. The decision to include or withdraw a participant from the study based on an ECG flagged as "Abnormal, Clinically Significant" is the responsibility of the investigator, in consultation with the MSD Clinical Director, as appropriate. The Fridericia (preferred) or Bazett correction method for calculating QTc will be used and recorded in the eCRF.

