### 10.6.2 Statistical Methods for Safety Analyses

Safety and tolerability will be assessed by clinical review of all relevant parameters including AEs, laboratory tests, vital signs, and ECG measurements.

Individual events and the broad AE categories consisting of the proportion of participants with any AE, a drug related AE, a serious AE, an AE which is both drug-related and serious, a Grade 3-5 AE, a drug related Grade 3-5 AE, a fatal AE, dose interruption due to an AE and discontinuation due to an AE, will be summarized by counts and percentages by treatment group (Table 18).

Table 18 Analysis Strategy for Safety Endpoints

Safety Endpoint	Descriptive Statistics
Any AE	X
Any Serious AE	X
Any Grade 3-5 AE	X
Any Drug-Related AE	X
Any Serious and Drug-Related AE	X
Any Grade 3-5 and Drug-Related AE	X
Dose Interruption due to AE	X
Discontinuation due to AE	X
Death	X
Specific AEs, SOCs	X
Change from Baseline Results (lab toxicity grade)	X

Abbreviations: AE = adverse event;

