## 12.4 Appendix 4: Adverse Events: Definitions and Procedures for Recording, Evaluating, Follow-up, and Reporting

### Definition of AE

#### AE Definition

- An AE is any untoward medical occurrence in a patient or clinical study participant, temporally associated with the use of study treatment, whether or not considered related to the study treatment.
- NOTE: An AE can therefore be any unfavorable and unintended sign (including an abnormal laboratory finding), symptom, or disease (new or exacerbated) temporally associated with the use of a study treatment.
- NOTE: for purposes of AE definition, study treatment includes any pharmaceutical product, biological product, vaccine, device, diagnostic agent or protocol specified procedure whether investigational (including placebo or active comparator product) or marketed, manufactured by, licensed by, provided by or distributed by the Sponsor or MSD for human use in this study.

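### Section 9.5.3 makes ECG findings adverse events from consent rather than from first dose, in conflict with three other parts of the protocol, and Section 10.6.2 has no onset rule to keep pre-dose findings out of Table 18

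*Combined protocol and SAP*

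**What the plan says.** Section 9.5.3 sorts ECG findings by consent. Those made earlier than consent go to the medical history. For the rest the rule is: "Clinically significant abnormal findings after signing consent should be recorded as an AE". On scheduling it says: "Baseline ECGs will be obtained at screening with additional ECGs obtained at EOT, and as clinically indicated for all participants". At select centres, Group 1 also has ECGs before and 2 hours after epacadostat on Day 1 of Cycles 1 and 2. The schedule in Section 2.1.1 agrees, in the row labelled "12-lead ECG (Local; Group 1 at select sites only".

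Other parts use different boundaries:

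- Section 9.5.1.1 makes a screening physical-examination abnormality medical history. "After the first dose of study treatment, new clinically significant abnormal findings should be recorded as AEs".
- Section 9.3.1 and Table 15 limit AE reporting between consent and randomisation to events during run-in treatment, events that cause exclusion, and events that result from a protocol-specified intervention. From randomisation the window opens fully: "All AEs from the time of treatment allocation/randomization through 30 days following cessation of study treatment must be reported by the investigator".
- Appendix 4 defines an AE as an occurrence "temporally associated with the use of study treatment, whether or not considered related to the study treatment". It excludes expected fluctuation of pre-existing conditions that do not worsen.

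For the analysis, Section 10.6.2 summarises "Individual events and the broad AE categories consisting of the proportion of participants with any AE" and other categories, by treatment group. It states no onset window.

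**The concern.** A screening ECG done for the protocol comes after consent and before any drug. Read alone, Section 9.5.3 makes a long-standing abnormality on it an AE, while the same person's screening physical-examination finding is medical history. A site cannot apply both as one rule.

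The Cycle 1 Day 1 pre-dose ECG matters more. It follows randomisation, so the reporting window does not screen it out, and only one arm has it on schedule. The analysis does not remove such a record either. The APaT population fixes which participants count, not which event dates count.

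Safety is the only secondary objective, and AEs are its first endpoint. What is at stake is a small number of pre-drug findings shown as on-study events in the specific-AE and system-organ-class rows, more readily in the experimental arm than elsewhere.

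**Working it through.** The plan gives no figure on this point, so there is nothing to reproduce. The check compares the texts and then scales the effect.

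**Step 1. One pre-existing ECG abnormality, not worsened, under each rule.**

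| Where seen | 9.5.3 | 9.3.1 | Appendix 4 exclusion |
|---|---|---|---|
| Routine ECG before consent, used for screening | Medical history | Outside the window | Not an AE |
| Protocol screening ECG | AE | Usually no report required | Points to not an AE |
| Cycle 1 Day 1 pre-dose ECG | AE | Inside the window | Points to not an AE |

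The second row is a conflict that the documents leave open. In the third row the reporting window gives no protection.

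**Step 2. Scheduled ECGs before the first dose.** Group 1 at select centres: 2 (screening and Cycle 1 Day 1 pre-dose). Group 1 elsewhere, Group 2 and Group 3: 1. Any arm may add clinically indicated ECGs, or repeats under the QTc exclusion criterion, which allows an average of 3.

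**Step 3. Weight of one record.** Section 10.9 gives arms of 36, 18 and 36, which sum to 90; 89 were randomised. One participant is 1/36 = 2.8 points, or 1/18 = 5.6 points in Group 2. The any-AE row moves only if that participant has no other AE.

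**Step 4. Possible Group 1 excess.** These inputs are assumptions, since the documents give none of them: p, the chance of a clinically significant finding on one ECG; f, the share of Group 1 at select centres; r, the correlation between the two readings. The chance of a clear screening ECG followed by a flagged Day 1 ECG is p(1 − p)(1 − r), so

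excess = 36 × f × p(1 − p)(1 − r).

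With r = 0 (independence), and f from 25% to 100%:

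- p = 2%: 0.0196 × 36 × f = 0.2 to 0.7 participants
- p = 5%: 0.0475 × 36 × f = 0.4 to 1.7
- p = 10%: 0.0900 × 36 × f = 0.8 to 3.2

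With r = 1 (a persistent abnormality, seen both times) the excess is 0. Table 18 counts participants, so a second sighting adds nothing.

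**Step 5. Condition on step 4.** The limit of zero supposes that a persistent abnormality is classified the same way at both recordings. If a site left it unreported at screening under 9.3.1 and then entered it on Day 1 under 9.5.3, the excess would be 36 × f × p. At p = 5% that is 36 × 0.05 × f = 0.45 to 1.8 participants. The Appendix 4 exclusion points against recording it that way.

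**The case against.** The strongest reply is that Section 9.5.3 should not be read alone. Section 9.3.1 and Table 15 govern the period before randomisation, and a chronic abnormality merely seen at screening normally meets none of their conditions. If it leads to exclusion, the person never enters APaT. This stands, and it removes most of the screening case.

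Appendix 4 also points against counting an unchanged pre-existing condition. That stands in part: its exclusion speaks of fluctuation, and its first bullet on qualifying events, which names ECGs, accepts clinical significance as sufficient and so leans towards Section 9.5.3.

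Recording events between randomisation and first dose is not peculiar to ECGs. Section 9.5.1.2 makes new findings on the directed examination AEs, and that examination precedes dosing at Cycle 1 in all arms. This stands, and it rules out declaring every pre-dose finding medical history. It does not supply the missing onset rule.

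Two stronger readings are tempting, and the documents support neither:

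- A reader might infer that baseline abnormalities pass straight into the AE tables of every arm. An assumed prevalence of 3% to 15% would give 36 × 0.03 to 36 × 0.15 = 1.1 to 5.4 participants per large arm. The documents give no prevalence, and the calculation ignores Section 9.3.1.
- A reader might infer that two pre-dose ECGs nearly double the false-AE chance, from 5% to 1 − 0.95² = 9.8%. That assumes independent readings, applies only at select centres, and does not fit a chronic abnormality. Eligibility ECGs fall within 10 days before first dose, so such a finding would tend to show on both.

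**Conclusion.** The contradiction is real. Section 9.5.3 uses a different boundary from Sections 9.5.1.1 and 9.3.1, lacks a new-or-worsened condition, and does not fit the Appendix 4 exclusion. For screening ECGs the passages conflict without settling the classification. For the Cycle 1 Day 1 pre-dose ECG, a pre-drug finding lies inside the AE window and can reach Table 18, and only Group 1 at select centres has that ECG on schedule.

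The likely effect is small: 2.8 points in a row per spurious record in a 36-person arm, with a Group 1 excess that tends to zero for persistent abnormalities seen at screening and handled alike both times. The independence figures of 0.2 to 3.2 participants show scale under assumed inputs and are not estimates. Drug-related rows should be spared, because the Appendix 4 causality guidance asks for a reasonable time sequence. ORR is unaffected, and no hypothesis is tested. The change is worth making because it is cheap and needs no new data.

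**What to change.** 1. Reconcile Section 9.5.3 with Sections 9.5.1.1 and 9.3.1 and Appendix 4, including its first bullet on qualifying events. An ECG abnormality already present at baseline and not worsened should be medical history. Keep the Section 9.3.1 reporting of new events from randomisation.
2. State in Section 10.6.2 that Table 18 counts AEs with onset or worsening on or after the first dose. Apply this with an onset flag and list earlier events separately. Do not recode AEs that investigators have reported.
3. Set the flag by ECG timepoint relative to dose, not by date alone. The pre-dose ECG and the first dose are both on Cycle 1 Day 1, so a date rule would keep the records it is meant to separate.

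The cost is a short rewording, one sentence in Section 10.6.2 and a derived flag for at most 89 participants, with no new assessment. Enrolment has stopped, so the benefit comes mainly from the analysis rule. The rule does not remove the extra post-dose ECGs in Group 1 at select centres, and ECG-related rows should be read with that in mind.

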#### 9.5.4 Clinical Safety Laboratory Assessments

Refer to Appendix 2 for the list of clinical laboratory tests to be performed and to the SoA for the timing and frequency.

- The investigator must review the laboratory report, document this review, and record any clinically relevant changes occurring during the study in the AE section of the CRF. The laboratory reports must be filed with the source documents. Clinically significant abnormal laboratory findings are those which are not associated with the underlying disease, unless judged by the investigator to be more severe than expected for the participant's condition.
- All protocol-required laboratory assessments, as defined in Appendix 2, must be conducted in accordance with the laboratory manual and the SoA.
- If laboratory values from non-protocol specified laboratory assessments performed at the institution's local laboratory require a change in study participant management or are considered clinically significant by the investigator (eg, SAE or AE or dose modification), then the results must be recorded in the appropriate CRF.
- For any laboratory tests with values considered clinically significantly abnormal during participation in the study or within 30 days for all AEs and 90 days for all SAEs (or 30 days following cessation of treatment if the participant initiates new anticancer therapy, whichever occurs first) after the last dose of study treatment, every attempt should be made to perform repeat assessments until the values return to normal or baseline or if a new baseline is established as determined by the investigator.

Laboratory tests for screening or entry into the Second Course Phase (Retreatment) should be performed within 10 days prior to the first dose of study treatment. Screening labs should be collected and assessed prior to randomizing the participant. After Cycle 1, pre-dose laboratory procedures can be conducted up to 72 hours prior to dosing. Results for specific laboratory tests (ie, complete blood count with complete differential, serum creatinine, electrolytes, and urinalysis) must be available and reviewed by the investigator or qualified designee and found to be acceptable prior to administration of each dose of study treatment.

Details regarding specific laboratory procedures/assessments to be performed in this study are provided below. The total amount of blood/tissue to be drawn/collected over the course of the study (from pre-study to post-study visits), including approximate blood/tissue volumes drawn/collected by visit and by sample type per participant can be found in the Laboratory Manual.

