Scheduled Window (Days):	-28 to -1	+5	±3	±3	±3	±3	At treatment discon	30 days after last dose (+7 days)	Assessments/procedures are to be performed on Day 1 and prior to the first dose of treatment for each cycle unless otherwise specified. Participants who discontinue study treatment for whatever reason will proceed directly to EOT and Safety Follow-up.
Hematology	X		X	X	X	X	X	X	Urinalysis and thyroid panel should be repeated every 2 cycles. Unresolved abnormal labs during the Safety Follow-up Visit that are TRAEs should be followed up as per sites' practices. .
Urinalysis	X		X		X	X	X	X	
Chemistry	X		X	X	X	X	X	X	
T3 (total or free), FT4 and TSH	X		X		X	X	X	X	
Hepatitis B and C Serology	X								Testing may be performed up to 40 days prior to randomization if performed as part of the standard documented clinical activities.
AE/SAE Review	X	X	X	X	X	X	X	X	Report non-serious AEs occurring within 30 days after the last dose of study treatment. Report SAEs occurring within 90 days after the last dose of study treatment, or 30 days after the last dose of study treatment if a new anticancer therapy is initiated, whichever is first.

Study Period	Screen	Treatment (3-week cycles)					EOT	Post-treatment	Notes
Treatment Cycle/Title	Screen (V 1)	1	2	3	4	Cycle 5 to Cycle 35	Discon	Safety FU	Assessments/procedures are to be performed on Day 1 and prior to the first dose of treatment for each cycle unless otherwise specified. Participants who discontinue study treatment for whatever reason will proceed directly to EOT and Safety Follow-up.
Scheduled Window (Days):	-28 to -1	+5	±3	±3	±3	±3	At treatment discon	30 days after last dose (+7 days)	
Patient Reported Outcomes (ePROs)									
EQ-5D		X	X	X	X				Prior to drug administration, AE evaluation, and disease status notification. Perform at every cycle through Cycle 4. Perform ePROs in the order listed in the SoA (EQ-5D first).
EORTC QLQ-C30		X	X	X	X				
EORTC QLQ-H&N35		X	X	X	X				

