**2.1.2 EXTREME Regimen Arm (Group 3)**

As of Amendment 04, after the Week 9 imaging assessment, participants can choose to discontinue from the study or continue study treatment as per protocol after participant discussion with the investigator and if they are receiving clinical benefits. For those participants remaining in the study, safety assessments are as per SoC. The SoA has been amended to only show the required assessments.

Study Period	Screen	Treatment (3-week cycles)															EOT	Post-treatment	Notes			
Treatment Cycle/Title	Screen (V1)	1			2			3			4			Cycle 5 Onwards			Discon	Safety FU				
Treatment Day		1	8	15	1	8	15	1	8	15	1	8	15	1	8	15	1	8		15		
Scheduled Window (Days):	-28 to -1	+5	±3	±3	±3	±3	±3	±3	±3	±3	±3	±3	±3	±3	±3	±3	Per Standard of Care	At treatment discon		30 days after last dose +7		
Administrative Procedures																						
Informed Consent	X																			Written consent must be obtained prior to performing any protocol-specific procedures.		
Participant Identification Card	X																					
Inclusion/Exclusion Criteria	X																			ECG and laboratory tests to determine eligibility are to be performed within 10 days prior to the first dose of study treatment. Screening labs should be collected and assessed prior to randomizing the participant.		
Demographics and Medical History	X																					
Disease Details	X																			HPV p16 status is required for participants with oropharynx as the primary tumor site.		
Prior/Concomitant Medication Review	X	X	X	X	X	X	X	X	X	X	X	X	X	X	X	X	X	X	X			

Study Period	Screen	Treatment (3-week cycles)															EOT	Post-treatment	Notes		
Treatment Cycle/Title	Screen (V1)	1			2			3			4			Cycle 5 Onwards			Discon	Safety FU			
Treatment Day		1	8	15	1	8	15	1	8	15	1	8	15	1	8	15	1	8		15	
Scheduled Window (Days):	-28 to -1	+5	±3	±3	±3	±3	±3	±3	±3	±3	±3	±3	±3	Per Standard of Care			At treatment discon	30 days after last dose +7	Assessments/procedures are to be performed on Day 1 and prior to the first dose of treatment for each cycle unless otherwise specified. Participants who discontinue study treatment for whatever reason will proceed directly to EOT and Safety Follow-up.		
Prior Oncological Treatment for HNSCC	X																				
Post-study Anticancer Therapy Status																	X	X			
Study Treatment Administration																					

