## 5. Study Design

### 5.1 Overall Design

**Note: Enrollment was stopped strategically on 02-MAY-2018. 89 participants were randomized in the study. As of Amendment 04, all study efficacy procedures will discontinue after first on-study imaging at Week 9 ( $\pm$  7 days); thereafter participants will be treated as per SoC for the disease and local guidelines. Safety procedures will continue as per protocol for all participants in Group 1 and 2 continuing study treatment. For Group 3 participants continuing study treatment after first on-study imaging at Week 9 ( $\pm$  7 days), safety procedures will continue as per SoC. The last study visit is the Safety Follow-up Visit. This section has been updated accordingly.**

This is a randomized, active-controlled, 3 parallel-groups, multi-site, open-label Phase 3 study evaluating pembrolizumab plus epacadostat, pembrolizumab monotherapy, and the EXTREME regimen in participants with R/M HNSCC who have not received prior systemic therapy for R/M disease. The EXTREME arm was selected as a comparator since it is the SoC per NCCN guideline, while the pembrolizumab monotherapy arm was included to identify the contribution of the individual components of the pembrolizumab plus epacadostat arm. The study has a primary endpoint of ORR. The study will be conducted in conformance with Good Clinical Practices (GCP).

The study includes a Screening period, a Treatment period, and a Post-treatment Safety Follow-up period. After signing the informed consent, candidate participants will be screened against all the eligibility criteria. Eligible participants will be centrally randomized in a 2:1:2 ratio and will be stratified based on:

- ECOG PS (0 vs. 1)
- HPV p16 expression status (either oropharynx-p16 positive vs. oropharynx-p16 negative or larynx/hypopharynx/oral cavity HNSCC); and
- Prior systemic oncological therapy (as part of the definitive treatment for locally advanced disease) (yes vs. no).

Originally, approximately 625 eligible participants with R/M HNSCC who meet the inclusion/exclusion criteria were to be enrolled in the study and centrally randomized in a 2:1:2 ratio in 3 treatment groups:

- Group 1: Pembrolizumab 200 mg 30-minute IV infusion Q3W  $\leq 35$  cycles plus epacadostat 100 mg PO BID  $\leq 35$  cycles
- Group 2: Pembrolizumab 200 mg 30-minute IV infusion Q3W  $\leq 35$  cycles
- Group 3: EXTREME regimen:

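### Section 9.5.4 makes four laboratory results a condition for every dose, but the Schedules of Activities do not schedule them before every dose

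*Combined protocol and SAP*

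**What the plan says.** **The rule.** Section 9.5.4 states: "Results for specific laboratory tests (ie, complete blood count with complete differential, serum creatinine, electrolytes, and urinalysis) must be available and reviewed". That task falls to the site physician or a delegate, and the results must also be "found to be acceptable prior to administration of each dose of study treatment". It adds: "After Cycle 1, pre-dose laboratory procedures can be conducted up to 72 hours prior to dosing". No arm, agent or cycle is exempted. The section also sends the reader "to the SoA for the timing and frequency", and requires protocol laboratory work to follow the SoA.

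**Groups 1 and 2 (Section 2.1.1).** Hematology and chemistry are marked at every cycle from Cycle 2. Urinalysis is marked at screening, Cycle 2 and Cycle 4, and the note says "Urinalysis and thyroid panel should be repeated every 2 cycles". The Second Course SoA (Section 2.2) carries the same note.

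**Group 3 (Section 2.1.2).** Hematology and chemistry are marked weekly from Cycle 1 Day 8 to Cycle 4 Day 15. Urinalysis is marked only at Cycle 2 Day 1 and Cycle 4 Day 1 after screening. The grid then hands all of these tests to SoC in the column for Cycle 5 onwards. The text above the grid puts the change after Week 9 imaging: "For those participants remaining in the study, safety assessments are as per SoC". Section 5.1 agrees that, for Group 3 after that imaging, "safety procedures will continue as per SoC", while Groups 1 and 2 stay on protocol procedures. The same grid allows platinum and 5-FU for up to 6 cycles and continues cetuximab weekly.

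**The analysis.** Table 18 (Section 10.6.2) lists a descriptive row, "Change from Baseline Results (lab toxicity grade", by treatment group. Section 10.5.2 asks for one post-dose value per parameter and sets no observation window.

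**The concern.** Section 9.5.4 gives a site two instructions that do not agree: have these results before each dose, and test when the SoA says. A site that does exactly what the SoA schedules departs from a stated pre-dose safety check at many doses, and sites may resolve the conflict differently.

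The gap is widest in Group 3 after the switch to SoC. The hold and restart rules for platinum and 5-FU (Sections 7.2.3 and 7.2.4) turn on neutrophils, platelets and creatinine. For the same doses, one passage makes the blood results mandatory and another leaves them to local practice.

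A second, separate matter is analytic. The arms are sampled at different frequencies, and more frequent sampling finds more abnormalities. This comes from the unequal schedules, not from the pre-dose sentence in Section 9.5.4.

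**Working it through.** The plan gives no figure to reproduce. The check counts scheduled doses against scheduled tests.

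**Inputs.** Up to 35 cycles in Groups 1 and 2 (Section 9.9.2). Up to 17 Second Course cycles (Section 7.2.6). Cetuximab on Days 1, 8 and 15 of each 21-day cycle (Section 9.1.9.1.3). Week 9 is 63 days from randomization, within 7 days either way (Section 9.2.1.2). Creatinine and electrolytes belong to the chemistry panel, and the differential to hematology (Appendix 2, Table 21).

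**Assumptions.** Screening laboratory tests, due within 10 days before the first dose, cover Cycle 1 Day 1. The every-2-cycles pattern continues on even cycles after Cycle 4.

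1. *Groups 1 and 2, urinalysis.* Even cycles from 2 to 34 number 17, and screening covers Cycle 1. Uncovered: 35 − 17 − 1 = **17 of 35** (Cycles 3, 5, …, 35). If screening is not counted, 18.
2. *Groups 1 and 2, hematology and chemistry.* Cycle 1 is covered by screening and Cycles 2 to 35 are each scheduled, so 0 of 35 are uncovered. For pembrolizumab the conflict is urinalysis only. Read literally, each dose would also include up to 35 × 21 × 2 = 1470 self-administered epacadostat doses, so the wording needs to say which administrations it means.
3. *Second Course, urinalysis.* If the tests fall on odd cycles, or on Cycle 1 and then even cycles, 9 are covered and 17 − 9 = 8 of 17 are not.
4. *Group 3, Cycles 1 to 4.* Weekly dosing visits: 4 × 3 = 12. Urinalysis covers Cycle 1 Day 1 (screening), Cycle 2 Day 1 and Cycle 4 Day 1. Uncovered: 12 − 3 = **9 of 12** (10 if screening is not counted), including the Cycle 3 platinum/5-FU dose. Hematology and chemistry are uncovered at 0 of 12.
5. *Group 3 from Cycle 5.* No test has a protocol schedule. Cycles 5 and 6 alone can hold 2 platinum/5-FU administrations and 2 × 3 = 6 cetuximab doses, and cetuximab may continue afterwards.
6. *Switch point.* Cycle 4 Day 1 nominally falls 3 × 21 = 63 days after Cycle 1 Day 1, which is Week 9 if treatment starts on the day of randomization. Under the text of Sections 2.1.2 and 5.1, Cycle 4 Days 8 and 15 are then under SoC. Under the grid they carry protocol tests.
7. *Blood draws by arm through Cycle 4, after the first dose.* Group 3: 12 − 1 = **11**. Groups 1 and 2: **3** (Day 1 of Cycles 2, 3 and 4). From Cycle 5 the pattern becomes SoC in Group 3 against every cycle in Groups 1 and 2.

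To illustrate item 7, assume independent visits, each with probability p of a graded abnormality. The documents give no p. The chance of seeing at least one is 1 − (1 − p)^k:

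| p | k = 3 | k = 11 |
|---|---|---|
| 2% | 6% | 20% |
| 5% | 14% | 43% |
| 10% | 27% | 69% |

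This shows the effect of sampling frequency alone. It does not predict trial results.

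**The case against.** The strongest reply is that this is only a conflict of wording. Section 9.5.4 itself defers to the SoA, Appendix 2 permits additional tests at any time, and moving Group 3 to SoC was a deliberate reduction under Amendment 04. Much of this stands. A reader might infer that the pre-dose check cannot be met, but a site can order extra tests. A reader might also infer that Group 3 has no laboratory tests from Cycle 5, but SoC may include all four; the documents do not say. What remains is that the SoA alone does not meet the rule, and that nothing tells a site which passage governs.

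On the analysis, a reader might infer that Table 18 compares worst grades over the whole treatment period and so biases the secondary objective. Neither a worst-grade rule nor that period is stated in Sections 10.5.2 or 10.6.2. The endpoints listed for the secondary objective are adverse events and discontinuations due to them (Section 4). The output is descriptive, and Section 10.8 rules out hypothesis testing.

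It is also tempting to think that limiting the laboratory summary to Cycles 1 to 4 would make the arms comparable. It would not: the 11-to-3 imbalance lies inside that window, and the text of Sections 2.1.2 and 5.1 disputes its last two Group 3 visits.

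**Conclusion.** The contradiction is real and sits in the current text. It affects urinalysis in every group and, in Group 3 after the switch to SoC, all four tests. Counting screening as cover for Cycle 1, 17 of 35 pembrolizumab cycles and 9 of 12 early Group 3 dosing visits have no scheduled urinalysis. The Group 3 switch point is stated in two ways. Sections 9.5.4, 2.1.1, 2.1.2, 2.2 and 5.1 must be reconciled; which tests should govern dosing is a clinical decision on which this review takes no position.

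The analytic consequence is smaller. Laboratory ascertainment differs by arm both before and after Week 9. Group 3 is sampled more often early and at an unspecified frequency later, so neither the size nor the net direction of any bias can be derived. The primary response-rate analysis is unaffected.

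**What to change.** 1. Reconcile Section 9.5.4 with Sections 2.1.1, 2.1.2, 2.2 and 5.1. The clinical team should decide which tests are conditions for dosing, for which administrations, and at which visits. The rule and all three SoA grids should then say the same thing.
2. State one switch point to SoC for Group 3, and say whether the pre-dose rule applies after it.
3. If the by-arm laboratory toxicity summary is to be read comparatively, report the number of laboratory assessments per arm and state the observation window. Show hematology and chemistry at the visits scheduled in every arm (Day 1 of Cycles 2, 3 and 4) alongside the summary of all data. Cycle 4 Day 1 qualifies only if the agreed switch point does not precede it.

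The cost is protocol wording and one additional safety display. The common-visit display leaves out the extra weekly draws in Group 3 and later toxicity, which is why it should accompany the full summary and not replace it.
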